2.9 Section 18 Statistical Considerations

18.1 Sample Size Calculations

Co-Primary Endpoint: Incidence Rate of *FVIII*-inhibitors ~~Inhibitory Antibodies against *FVIII*~~ Defined as ~~Titre~~ ≥ 0.6 BU/mL

Given the rarity of the disease, a sample size of 105 patients treated for a minimum of 50 exposure days will allow for a reasonable evaluation of inhibitor formation in this pivotal trial.

The aim is to demonstrate that the upper confidence limit for the inhibitor rate is below 6.8%. In practical terms this will happen if 2 or less inhibitors are observed in the planned 105 patients with 50 exposure days (3 or less if the trial should end with 127 patients with 50 EDs). If the true inhibitor rate of N8-GP is 0,5 ±% then the chance/power to achieve a maximum of 2 inhibitors out of 132 patients entered into the trial will be ~~85%~~ 97%.

Co-Primary Endpoint: Annualised bleeding rate in the prophylaxis arm

The clinical efficacy of N8-GP in long term bleeding prophylaxis will be evaluated based on all the prophylaxis period data. This will give different period lengths for the different patients but on average it is expected to give about 12 month prophylaxis treatment per patient (~7 months for the last recruited patients and ~17-19 months for the first recruited patients). Prophylactic effect will be concluded if the upper 97.5% confidence limit for the annualised bleeding frequency is < 8.5.

Annualised bleeding rate for withdrawals will be imputed for the missing period based on their observed bleeding rate except for patients withdrawn within one month where imputation will be performed based on an annualised bleeding rate of 24. The true bleeding rate will be assumed to be 6.8 as for historical prophylaxis data but for the sample size calculation it will be assumed that 1 patient will withdraw within 1 month and that will lift the effective annualised bleeding rate for the power calculation by $24/120 = 0.2$, i.e. from 6.8 to 7.0.

The model will be a Poisson regression allowing for over-dispersion (using Pearson's chi-square divided by the degrees of freedom (i.e. Scale=Pearson in SAS)) and using log observation time as offset to account for the differing treatment lengths. Based on an approximation to the normal distribution and assuming that the patients bleed 7.0 ~~6.8~~ times per year and an over-dispersion of 5 (so variance ~~34~~ 35) 120 patients entered on prophylaxis will give a power of ~~89%~~ 79%.

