For patients continuing in pathfinderTM2 with inhibitor (≥ 0.6 and ≤ 5 BU/mL): the patient must follow per-protocol treatment schedule and the scheduled visits as described in Flowchart Table 2-1 and Table 2-3. Additional visits can be scheduled if closer monitoring is needed. Closer monitoring is highly recommended but this decision will be at Investigator's discretion. In the event of a concern about reduced treatment efficacy a PK session may be performed. The PK can be evaluated after a wash out period of at least 96 hours. Blood sampling during the PK profile session can be performed at the following time points: pre-dose, 30 minutes (± 10 min), 24h (± 8 hours), 48h (± 8 hours), 72h (± 8 hours) and 96h (± 8 hours).

A confirmed positive inhibitor is considered to have disappeared if the inhibitor titre is < 0.6 BU/mL on 2 consecutive inhibitor tests (performed at 2 consecutive visits) and the FVIII recovery is $\geq 66\%$ of expected values. A patient with repeated positive inhibitor test result will count only once in the determination of the inhibitor incidence rate.

Patients who develop an inhibitor should be classified as high responders (peak inhibitor titre > 5 BU/mL), low responders (peak inhibitor titre ≤ 5 BU/mL), and whether the inhibitor is transient (disappearing (inhibitor titer < 0.6 BU/mL on ≥ 2 consecutive measurements) spontaneously within 6 months without a change in treatment regimen), or not.

...

An inhibitor test with a result ≥ 0.6 BU/ml will be considered as a positive inhibitor test. A patient is verified inhibitor positive if two independent samples from *the* same patient are inhibitor positive

Protocol Amendment
Trial ID: NN7088-3859
UTN: U1111-1119-7416
EudraCT No.: 2011-001142-15

~~CONFIDENTIAL~~

Date:	29 November 2013	Novo Nordisk
Version:	1.0	
Status:	Final	
Page:	12 of 14	

(≥ 0.6 BU/mL) – and the patient *may* discontinue the trial including an EOT Visit and FU Visits *or* remain in *pathfinderTM2* as described above.

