1.2 Scope of the statistical analysis plan

The scope of this SAP is to clarify the planed analysis for extension phase part 2 described in the protocol.

This SAP is based on the Protocol *A Multi-national Trial Evaluating Safety and Efficacy, including Pharmacokinetics, of NNC 0129-0000-1003 when Administered for Treatment and Prophylaxis of Bleeding in Patients with Haemophilia A* version 1.0 (30-Sep-2011) including Final Substantial Amendment no 1 version 1.0, NL (24-Oct-2011), Final Substantial Amendment no 2 version 1.0, Global (09-Dec-2011), Final Substantial Amendment no 5 version 1.0 FR (3-Feb-2012), Final Substantial Amendment no 6 version 1.0, Global (30-Mar-2012), Final Substantial Amendment no 8 RU (21-Jun-2012), Final Substantial Amendment no 10 version 2.0, Global (03-Dec-2012), Final Substantial Amendment no 11 version 1.0 IL (05-Dec-2012), Final Substantial Amendment no 12

Statistical Analysis Plan
Trial ID: 7088-3859-final
UTN: U1111-1119-7416
EudraCT No.: 2011-001142-15

~~CONFIDENTIAL~~

Date:	14 January 2019	Novo Nordisk
Version:	1.0	
Status:	Final	
Page:	5 of 25	

version 1.0, Global (05-Mar-2013), Final Substantial Amendment no 13 version 1.0, Global (03-May-2013), Final Substantial Amendment no 14 version 1.0, Global (12-Jul-2013), Final Substantial Amendment no 15 version 1.0, Global (28-Aug-2013), Final Substantial Amendment no 18 version 1.0, Global (29-Nov-2013), Final Substantial Amendment no 19 version 2.0, Global (29-Apr-2016), and the final version of the protocol for this trial (version 13, 24 January 2017).

2 Statistical considerations

The Pivotal part of the trial was reported based on all data from the Main Phase where all patients have reached at least 50 EDs (except for patients having had surgery as part of pathfinder™3), and all patients have had their first visit after 50 EDs where all planned assessments including inhibitors have been performed. All main conclusions from the trial are based on this reporting except for conclusions regarding every 7 day prophylaxis and long term safety/efficacy.

In the interim at end of extension phase part 1 all data from main phase up to the end of extension phase part 1 was analysed and reported. The main focus was on once weekly prophylaxis with every 4 day dosing as control where patients with low bleeding rate could be randomised to the two treatment arms.

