2.2.2 Primary Endpoint(s)

The study has two co-primary endpoints that both have to succeed.

Incidence Rate of FVIII-inhibitors ≥ 0.6 BU

The rate of inhibitors will be reported and a 1-sided 97.5% upper confidence limit will be provided based on an exact calculation for a binomial distribution. For the calculation of the inhibitor rate the nominator will include all patients with neutralising antibodies while the denominator will include all patients with a minimum of 50 exposures plus any patients with less than 50 exposures but with neutralising inhibitors. Adequate safety with regard to neutralising inhibitors will be concluded if the upper 1-sided 97.5% confidence limit is below 6.8% roughly corresponding to the upper 97.5% confidence limit if 2 inhibitors out of 105 patients are observed (3 or less if the study should get 127 or more patients with 50 exposure days).

Annualised bleeding rate (total number of bleeding episodes per patient assessed as annualised bleeding rate) in the prophylaxis arm

A review of historical data has found that haemophilia A patients on on-demand treatment on average bleed 24 times per year while they bleed 6.8 times per year when treated on prophylaxis.

Historical Control for Hypothesis Test for Prophylaxis

Based on the studies referenced below, Novo Nordisk suggests that representative numbers for mean annual bleeding rate (ABR) in severe haemophilia patients is 24 bleeds/year for patients treated on-demand and 6.8 for patients on prophylactic treatment.

Novo Nordisk has based the estimate of historical annual bleeding rate on a systematic review of the treatment of Haemophilia A and B and von Willebrand disease, performed by the Swedish Council on Health Technology Assessment.

The referenced report is based on review of 3710 abstracts in total, covering treatment of Haemophilia A, B or von Willebrand disease. Articles were then selected for full review according to specific criteria such as administration of recombinant or plasma-derived Factor concentrate, outcome (eg number of bleeding episodes, inhibitor development or quality-of-life measurements), and number of patients included. For haemophilia A, only studies comprising 20 patients or more were selected. The main objectives of the SBU review is to evaluate the short- and long-term effects

with different treatment strategies with coagulation factor concentrates in Haemophilia A and B and von Willebrand disease.

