Only treatment requiring bleeding episodes will be considered in the above evaluations of ABR. Incidence rate of FVIII-inhibitor and haemostatic effect of N8-GP when used for treatment of bleeding episodes will be evaluated based on accumulated data (Main Phase + Extension Phase part 1).

Adverse events, consumption of N8-GP, recovery and pre-dose levels will be summarised based on accumulated data (Main + Extension Phase part 1) by treatment regimen combining the every 4 day dosing regimens. In addition, separate summaries including data from part 1 only will be presented by treatment regimen for the randomised subset of patients to support the main objective of part 1 of the Extension Phase.

Other safety endpoints will be summarised based on accumulated data (Main Phase + Extension Phase part 1). Binding non-inhibitory antibodies will be listed.

PRO endpoints at end the Extension Phase part 1 will be evaluated and presented as described in section 18.9.

Data from part 2 of the Extension Phase

The main objective of extension phase part 2 is to collect long term safety and efficacy data.

ABR will be calculated as for the co-primary endpoint in the main phase, but based on the accumulated data, i.e. combined data from main phase, extension phase part 1 and extension phase part 2. Furthermore, sensitivity analyses are performed based on actual bleeding episodes and exposure times (i.e. without imputation for withdrawn patients).

Incidence rate of FVIII-inhibitor and haemostatic effect of N8-GP when used for treatment of bleeding episodes will be evaluated based on accumulated data.

Adverse events and consumption of N8-GP will be summarised based on accumulated data by treatment regimen.

Incremental recovery will be summarised by visit for extension phase part 2 and furthermore be presented graphically in the following ways:

- By N8-GP production process (extension phase part 2 data)
- According to Anti-PEG-antibody status (accumulated data)

For Anti-CHO HCP-antibodies, the number of negative/positive samples will be summarised by visit.

Other safety endpoints will be listed and/or plotted based on accumulated data.

-

PRO endpoints for extension phase part 2 will be summarised by time since first dose (since timing of visits depend on treatment regimen). Time grouping will span a year, i.e. grouping being “1 - <2 years”, “2 - <3 years”,.... The two prophylaxis regimens will be considered as a combined prophylaxis treatment regimen.

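### On accumulated data the inhibitor incidence rate is a proportion of patients with no exposure time in it, so it cannot show whether long-term risk is rising, constant or falling

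*SAP*

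**What the plan says.** SAP 2.2.2 gives the inhibitor rate as a proportion of patients. The numerator is all patients with neutralising antibodies, and "the denominator will include all patients with a minimum of 50 exposures plus any patients with less than 50 exposures but with neutralising inhibitors". The limit is "based on an exact calculation for a binomial distribution". Protocol 8.3.2.2, as amended in November 2013, adds: "A patient with repeated positive inhibitor test result will count only once in the determination of the inhibitor incidence rate".

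The decision rule in SAP 2.2.2 reads: "Adequate safety with regard to neutralising inhibitors will be concluded if the upper 1-sided 97.5% confidence limit is below 6.8" (per cent). It is tied to 2 cases in 105 patients, or "3 or less if the study should get 127 or more patients with 50 exposure days".

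For the extension, SAP 2.10 says of part 2: "Incidence rate of FVIII-inhibitor and haemostatic effect of N8-GP when used for treatment of bleeding episodes will be evaluated based on accumulated data". It makes the same statement for main phase plus part 1, as does Protocol 18.10. Neither place gives a person-time, per-exposure-day or time-to-event version, or a new limit.

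SAP section 2 rests the main conclusions on the pivotal reporting, "except for conclusions regarding every 7 day prophylaxis and long term safety/efficacy". SAP 2.10 names long-term safety and efficacy data as the main objective of part 2.

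**The concern.** The 50-exposure rule is a floor. It does not adjust for length of follow-up. At one dose every 4 days, 50 exposures take about 200 days, and a patient with that much exposure counts the same as one treated for five years. Each case counts once, and no rule removes a case whose inhibitor later disappears. Once all patients who will reach 50 exposures have done so, the figure can only stay level or go up.

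Part 2 is meant to show what happens to risk under long exposure. A later proportion above the pivotal one is expected if the yearly risk is constant, and it is possible even if that risk is falling. A reader would have no means of telling these apart from a true increase.

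The SAP recognises the issue elsewhere. Bleeding is modelled with log observation duration as an offset (2.2.2). Bleeding rates for part 2 alone are dropped because patients enter it with differing trial durations (section 3). Patient-reported outcomes in part 2 are grouped by time since first dose (2.10). The inhibitor endpoint has no such provision.

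**Working it through.** **Inputs from the documents**
- Success limit: upper 1-sided 97.5% exact binomial limit below 6.8% (SAP 2.2.2).
- Assumed true rate 0.5%, applied to 132 patients entered, stated power 97% (Protocol 18.1, Amendment 6: "If the true inhibitor rate of N8-GP is 0,5", in per cent). No time base is attached to the 0.5%.
- Planned prophylaxis completers: 105, or 145 if the sample size was increased (Protocol 5.1).
- First patient first visit 01-Feb-2012 and planned last visit 03-Dec-2018 (Protocol 7); part 2 cut 15-Aug-2017 (SAP 2.5).

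**Plan's own figures**
- P(X ≤ 2 | n = 132, p = 0.005) = 97.1%, against the stated 97%.
- Exact upper limits: 2/105 = 6.71%, 3/105 = 8.12%, 3/126 = 6.80% (just above the limit), 3/127 = 6.75%. The stated acceptance counts reproduce.
- For 145 patients: 3/145 = 5.93%, 4/145 = 6.91%, so at most 3 cases.

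The permitted count depends on the number of patients only. It does not grow with follow-up.

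**Longest possible follow-up**
- 01-Feb-2012 to 15-Aug-2017: about 5.5 years.
- 01-Feb-2012 to 03-Dec-2018: about 6.8 years.

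**Illustration, under assumptions not in the documents**

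Assume a constant yearly risk r, with everyone followed for T years. The cumulative risk is p(T) = 1 − (1 − r)^T. The chance of meeting 6.8%, if that rule were applied, is P(X ≤ 2) for n = 105 and P(X ≤ 3) for n = 145.

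| r per year | T (years) | p(T) | n = 105 | n = 145 |
|---|---|---|---|---|
| 0.5% | 1 | 0.50% | 98% | 99% |
| 0.5% | 3.5 | 1.74% | 72% | 75% |
| 0.5% | 4.5 | 2.23% | 58% | 59% |
| 0.5% | 5.5 | 2.72% | 45% | 44% |
| 0.25% | 4.5 | 1.12% | 89% | 92% |

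The risk per year is the same at every T within each value of r. At the 2017 cut, 5.5 years is the maximum follow-up, so that row is a bound and not a plausible mean. Drop-out or risk concentrated early would make the fall smaller.

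**The same data with time in the denominator**

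The rate is x / patient-years, with exact Poisson upper 97.5% limit χ²(0.975; 2(x+1)) / (2 × patient-years). For 145 patients:
- 1 case in 145 × 1 = 145 patient-years: 0.69 per 100 patient-years, upper limit 3.84.
- 4 cases in 145 × 5 = 725 patient-years: 0.55 per 100 patient-years, upper limit 1.41.

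As proportions these are 1/145 = 0.7% and 4/145 = 2.8%. The proportion quadruples while the rate per patient-year falls slightly and its upper limit tightens.

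**The case against.** A reader might infer that the plan re-tests the 6.8% limit on accumulated data, so that follow-up alone could reverse the safety conclusion. The documents do not support that. The introduction to Protocol section 18 (Amendment 13) assigns 18.1 to 18.9, which include the 6.8% rule, to the Main Phase and puts the extension methods in 18.10. Protocol 18.1 and SAP 2.1 tie the co-primary endpoints to the Main Phase or pivotal part. Where the SAP wants a decision rule used again it says so: 2.10 restates the 8.5 bleeding limit for every 7 day dosing and restates nothing for inhibitors. What remains is a wording gap, because SAP 2.2.2 gives the rule without confining it to the pivotal part, and SAP section 2 leaves long-term safety conclusions open.

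The size can also be challenged, and that challenge stands. The 0.5% has no time base, the constant hazard is not in the documents, mean follow-up is not stated, and giving everyone equal follow-up is a simplification.

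Third, Protocol 4.2.4 and section 18 already promise safety endpoints by phase as well as accumulated, which is part of the remedy. However, inhibitors are listed as a co-primary endpoint and not under the safety endpoints in 4.2.2.3. SAP section 3 also reduces safety output other than adverse events to listings and individual plots, so it is unclear that the promise covers them. Separate proportions by phase would still carry no exposure time.

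Finally, a cumulative proportion is the prespecified endpoint, and any cumulative measure is unable to fall. That is a good reason to keep it, but it does not make it informative about long-term risk.

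**Conclusion.** The point holds as a limitation of the accumulated analysis. The one inhibitor measure defined in the SAP ignores very unequal follow-up and cannot answer the long-term safety question that part 2 is meant to address. The pivotal test, its limit and its power reproduce and are unaffected, and no planned confirmatory conclusion changes.

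The direction of the problem follows from the definition alone. Its size does not. The rise from 0.5% to 2.2%, and the fall in the chance of meeting 6.8% to 58% or 59%, need a constant 0.5% per year and 4.5 years of follow-up for everyone. The second figure also needs a 6.8% verdict that the documents do not call for. At half that yearly risk the chance is 89% or 92%. These figures are illustrations, not forecasts.

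**What to change.** In SAP 2.10, add first confirmed inhibitors per 100 patient-years and per 1,000 exposure days, with exact Poisson limits. Count from first dose to the first confirmed positive test or the last inhibitor test, and split the result at the pivotal cut so that early and late risk can be compared. Keep the proportion as a descriptive line. In SAP 2.2.2, state, in line with Protocol section 18, that the 6.8% rule applies only to the pivotal analysis.

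The cost is a few sentences and a few table rows from dosing and testing dates already held, with no new assessments. With few events the limits will be wide, especially after the split, and the report should say so.

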Prophylactic effect of N8-GP will be concluded if the bleeding rate is significantly below 50% of the historical on-demand bleeding rate (i.e. significantly lower than 12) as well as within 25% of the historical prophylaxis bleeding rates (i.e. significantly lower than $6.8 * 1.25 = 8.5$). Since both must be met in practice it must be shown that the bleeding rate is significantly lower than 8.5.

Let AR be the true yearly bleeding rate. The null-hypothesis will be tested against the alternative hypothesis as given by:

$H_0: AR \geq 8.5$ against $H_A: AR < 8.5$

The endpoint will be analysed by a Poisson regression model on number of bleeding episodes per patient allowing for over-dispersion (using Pearson's chi-square divided by the degrees of freedom (i.e. $Scale = P_{scale}$ in SAS)) and using log observation duration as an offset. Estimates of the annualised bleeding rates will be provided with 95% confidence intervals.

For patients withdrawing prematurely, the number of bleeding episodes counting in the analysis will be imputed up to what they could be expected to have had if they had completed the trial. If e.g. a patient withdraws after 2 months with 3 bleeding episodes, but the patient should have been in the study for 12 months, then this patient will in the analysis count as having had 18 bleeding episodes in 12 months. This is similar to last observation carried forward (LOCF) and will avoid positive bias occurring from patients with many bleeding episodes withdrawing early.

The rules for calculating planned exposure time used for imputation depends on what part of the trial the patient is withdrawn from and furthermore what parts of the trial the calculations represent as described in the following.

Calculations of ABR for the Pivotal part:

Since the planned exposure time for each patient in the Pivotal phase of the trial depends on when the patient was recruited in the trial, the maximum expected exposure time based on the last visit date included in each part of the analysis will be used as planned exposure time, e.g. the date of the last patient's first visit after his 50EDs will be used for the pivotal part of the analysis where all patients should have reached at least 50 EDs (except for patients having had surgery as part of pathfinder™3).

Calculations of ABR for extension phase part 1:

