2.3 Safety Endpoints

Adverse Events (AEs) and Serious Adverse Events (SAEs) reported during the trial

Treatment emergent AEs (TEAEs defined as AEs occurring after dosing with trial product) and treatment emergent SAEs (TESAEs) will be summarised by frequency of events and frequency of patients with any event. Similar summaries cross-classified by severity and by causal relation to trial product will be made.

Furthermore, listings will be provided displaying all TEAEs and TESAEs including pertinent clinical information.

Changes in vital signs (blood pressures, pulse, temperature, respiratory rate)

These endpoints will be presented and listed

Other safety parameters

All additional safety parameters such as laboratory parameters, vital signs and physical examinations will be presented and listed.

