Calculation of ABR by month for a given treatment regimen has been defined to be based on the first consecutive period on the treatment regimen to ensure that a effect over time is not influenced by time on other treatment regimens.

Calculation of ABR by calendar month has been defined to be done by shifting calendar month half a year for countries in the southern hemisphere (i.e. Brazil and Australia). This is done to take the difference in seasons between the southern and northern hemisphere into account.

The ABRs defined to be calculated based on a sub-selection consisting of data from extension phase part 2, will not be done, since patients have differing trial durations when entering extension phase part 2 and therefore ABRs for such a sub-selection is of limited value.

PK data:

Since patients are allowed to change treatment regimen at any time during the extension phase part 2 and since the visits intervals are different for the prophylaxis treatment regimens, FVIII activity data will be summarised by visit only for incremental recovery. Since incremental recovery is dose-normalised activity increase this will not be affected by a possible regimen and dose change.

Plots of pre-dose activity measurements will not be created since the plots have been evaluated to contribute with no relevant information.

PRO data:

PRO endpoints for extension phase part 2 will be summarised by grouping of time since first dose, since timing of visits depend on treatment regimen and since patients are moving between treatment regimens.

Safety data:

Adverse Events and Serious Adverse Events will be summarised by treatment regimen and all other safety endpoints will be presented by listings and individual graphical representation only. Safety data consists of accumulated data from the trial.

4 References

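### The accumulated by-regimen AE and SAE summary specifies no exposure-adjusted rate and no rule for assigning an event to a regimen after a switch, so its columns mix time on regimen with risk

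*SAP*

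**What the plan says.** SAP 2.3 sets the metric: treatment-emergent AEs and SAEs are "summarised by frequency of events and frequency of patients with any event". Treatment-emergent means after dosing with trial product; the definition does not refer to the regimen in use when the event began.

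SAP 2.10, for extension part 2, sets the grouping and the data: "Adverse events and consumption of N8-GP will be summarised based on accumulated data by treatment regimen". Accumulated here means main phase plus extension parts 1 and 2. SAP section 3 repeats this for the end of the trial ("Adverse Events and Serious Adverse Events will be summarised by treatment regimen") and leaves all other safety endpoints to listings and individual plots.

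Elsewhere the SAP does allow for time on treatment or for switching:

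- The annualised bleeding rate (ABR) is modelled "using log observation duration as an offset" (SAP 2.2.2).
- Consumption is given per month and per year (SAP 2.2.4).
- FVIII activity by visit is cut back to incremental recovery: "Since patients are allowed to change treatment regimen at any time during the extension phase part 2" is one of the reasons (SAP section 3).
- Patient-reported outcomes are regrouped by time since first dose, "since timing of visits depend on treatment regimen and since patients are moving between treatment regimens" (SAP section 3).
- ABRs restricted to part 2 are dropped, "since patients have differing trial durations when entering extension phase part 2" (SAP section 3).

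No matching provision is made for AEs.

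**The concern.** A frequency of events, or of patients with any event, grows with the time observed. If one column collects more time per patient than another, the two differ even when the yearly risk is the same. Here the times differ by design, and a patient who moves to weekly dosing contributes to two columns. Without an onset rule, two programmers could place the same event in different columns.

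The table carries weight. SAP section 2 rests the main conclusions on the pivotal report, but exempts conclusions on every-7-day prophylaxis and on long-term safety and efficacy. SAP 2.10 names long-term safety and efficacy as the objective of part 2. With the other safety endpoints confined to listings and plots, the AE and SAE summary is the main tabulated safety evidence by regimen at the end of the trial. Readers will set its columns against each other whether or not the plan calls that a comparison.

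**Working it through.** The documents give no AE rate, AE precision target or AE power, so there is no planned figure to reproduce. The check asks how far apart two columns can be when the true rate is the same.

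**Inputs from the documents**

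- Main-phase prophylaxis exposure averages more than 1 year (protocol 5.1) and is at most 100 weeks (SAP 2.2.2): 100 × 7 / 365.25 = 1.92 years.
- The planned randomised period of extension part 1 is 24 weeks (SAP 2.2.2): 24 × 7 / 365.25 = 0.46 years.
- Weekly dosing begins only in the extension (SAP 1.1).

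**Assumptions**

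- A constant AE rate r, equal in both regimens, at 0.5, 1 or 2 per patient-year. The documents give no value.
- The same time t for every patient in a column. Realised time on each regimen is not in the documents.

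**Formulas**

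- Expected events per 100 patients = 100 × r × t
- Proportion with any AE = 1 − exp(−r × t)
- Exposure-adjusted rate = events / patient-years = r

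**Example at r = 1, 1.00 v 0.46 years.** Events per 100 patients: 100 v 46, ratio 1.00 / 0.46 = 2.17. Any AE: 1 − exp(−1.00) = 63% v 1 − exp(−0.46) = 37%.

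**Equal true risk in both regimens**

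| Years, every 4 days v weekly | Event ratio | Any AE, r = 0.5 | r = 1 | r = 2 |
|---|---|---|---|---|
| 1.00 v 0.46 | 2.17 | 39% v 21% | 63% v 37% | 86% v 60% |
| 1.46 v 0.46 | 3.17 | 52% v 21% | 77% v 37% | 95% v 60% |
| 2 v 4 (assumed) | 0.50 | 63% v 86% | 86% v 98% | 98% v 100% |

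The second row adds 24 weeks of every-4-day dosing to one year of main phase. The third is a patient who spends most of the extension on weekly dosing. It is possible on the planned dates (first visit 01-Feb-2012, last visit 03-Dec-2018, 6.8 years), and it reverses the direction.

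The event ratio is the ratio of the times and does not depend on r. The percentages depend on r and on the constant-rate model. In every row the exposure-adjusted rates have ratio 1.00.

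**A true difference can also be masked.** Take 1.00 v 0.46 years with the weekly rate doubled. Any AE becomes 1 − exp(−r) v 1 − exp(−2 × r × 0.46): 39% v 37% at r = 0.5, 63% v 60% at r = 1, and 86% v 84% at r = 2.

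**The case against.** The strongest reply is that this is a descriptive table. AEs are to be summarised, and no test, ratio or threshold is attached to them. Where the SAP wants a contrast between regimens it says so, as for the ABR ratio in part 1. That stands: a reader might infer a planned AE comparison, and the documents contain none. The columns will still be read side by side.

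Second, raw counts and percentages are the natural reading of SAP 2.3, but the documents contain no AE table shells. What can be supported is that no exposure-adjusted rate is specified.

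Third, safeguards exist. SAP 2.10 plans a part-1-only AE summary by regimen for the randomised subset, with 24 weeks planned in both arms. Protocol 18.10 plans a summary of time on each prophylaxis regimen in part 2. All treatment-emergent events are listed. These reduce the problem. However, the subset summary is short and weekly patients can leave that arm early, while the time summary covers part 2 only and is not tied to the AE table. Neither supplies a rate for the accumulated data.

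Fourth, it is tempting to say that weekly dosing will look safer because it has less time. The documents do not support that. Weekly dosing can continue through part 2, switching back is compulsory only under the bleeding rule, and realised time by regimen is not given.

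**Conclusion.** The point holds as a gap in specification. The accumulated by-regimen AE and SAE summary has no exposure-adjusted rate and no regimen-at-onset rule, although time on regimen differs by design and patients switch. With equal risk and 1.00 year against 24 weeks, events per patient differ about 2.2-fold and the proportion with any AE differs by 18 to 26 percentage points over the assumed rates (39 − 21 = 18; 63 − 37 = 26; 86 − 60 = 26). These sizes are illustrations: the AE rate and the realised time on each regimen are assumptions, and other divisions of time reverse the sign.

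Two stronger readings should be set aside. The table does not reflect exposure instead of risk; it mixes the two in unknown proportion. Nor would rates make the regimens comparable. Entry to weekly dosing is limited to patients with 0-2 bleeds in 6 months and follows earlier every-4-day exposure, so differences between the rates would still not be causal.

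**What to change.** In SAP 2.3, 2.10 and section 3:

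1. Assign each AE and SAE to the regimen in use at onset.
2. In every by-regimen AE and SAE table, add patient-years on that regimen and events per patient-year beside the frequencies.
3. Use actual time on regimen, excluding time in the surgery and PK trials. The exposure behind the main ABR analysis should not be reused as it stands, because for withdrawn patients it runs to a planned end date. The no-imputation ABR analysis in SAP 2.10 already needs actual exposure and is the better source.
4. State that the rates are descriptive, because entry to weekly dosing is limited to patients with 0-2 bleeds in 6 months, and that one patient can appear in more than one column.

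No new data are needed. The cost is slightly longer tables and an onset-to-regimen derivation.
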